#### **4.5 SURGICAL TECHNIQUE**

All surgical procedures were performed by a team composed of two trained and calibrated surgeons, exclusively during the morning period. Each patient was treated by the same surgeon for both surgical procedures. A standardized surgical protocol was applied in all cases and included anamnesis, clinical examination, and collection of vital signs (blood pressure and heart rate).

Patients were positioned in the dental chair and underwent antisepsis of the oral cavity and adjacent extraoral region using 0.12% aqueous chlorhexidine. After establishment of a sterile surgical field, local anesthesia was administered via inferior

alveolar, lingual, and buccal nerve blocks using 2% mepivacaine with 1:100,000 epinephrine. A mucoperiosteal incision was made extending from the retromolar area to the mesial aspect of the second molar, with a relaxing incision in an open L-shaped design to expose the underlying bone. Under copious saline irrigation, osteotomy was performed in the distobuccal region using a #6 round bur, and odontosection was carried out when necessary using a 702 surgical bur. Following tooth removal, wound closure was achieved with simple interrupted sutures using 4-0 silk sutures.

Prior to the first surgical procedure, maximum mouth opening was measured in millimeters using a measuring tape to determine the interincisal distance. In cases where maxillary or mandibular incisors were absent, the occlusal edges were used as reference points. This measurement was used as a baseline parameter for comparison between procedures.

#### **4.6 POSTOPERATIVE CARE**

In the immediate postoperative period following the first surgical procedure, the allocation of postoperative care—with or without cryotherapy—was randomized using a simple draw. Allocation was determined by the selection of a folded paper indicating Group A or Group B and was supervised by a third party to ensure allocation concealment. When the first surgical site of a patient was assigned to Group A (control), the contralateral site in the second surgical procedure was assigned to Group B (test), and vice versa.

Group A (control) did not receive postoperative cryotherapy. Group B (test) was instructed to apply standardized ice packs (11 × 8.5 × 1 cm), provided by the research team, positioned diagonally to cover both the mandibular angle and the cheek on the operated side. Cryotherapy was initiated immediately after surgery under surgeon supervision and continued for the first 12 postoperative hours, consisting of 30-minute applications followed by 30-minute intervals (total of 12 applications). During the intervals, patients were instructed to store the ice packs in a freezer until the next application.

All participants received identical pharmacological postoperative instructions (APPENDIX B) for both interventions, including paracetamol 1 g every 6 hours for 3 days and mouth rinses with 0.12% aqueous chlorhexidine digluconate twice daily for 7 days, starting on the day following surgery. In cases of persistent pain, trismus, or edema that significantly interfered with daily activities despite the use of prescribed analgesics, patients were instructed to use rescue medication consisting of codeine 30 mg every 4 hours as needed.

## 4.7 STUDY VARIABLES

The outcome variables of this study were postoperative pain, trismus, local edema, and changes in quality of life following mandibular third molar extraction. Postoperative assessments were performed by the research team, consisting of two calibrated surgeons and one supervising professor, on postoperative days 0 (day of surgery), 2, and 7. The following evaluation protocols were applied:

a) Pain assessment: postoperative pain was assessed using a visual analog scale (VAS– APPENDIX C) ranging from 0 to 10, in which 0 represented no pain, 1–3 mild pain, 3.1–6 moderate pain, and 6.1–10 severe pain. Patients completed the scale at home daily until postoperative day 7.

b) Trismus assessment: trismus was evaluated by measuring maximum mouth opening with the patient seated and the tragus–ala plane parallel to the ground. Patients were instructed to open their mouths three consecutive times, and the mean value was recorded. Measurements were obtained as the interincisal distance in millimeters using a measuring tape. In the absence of maxillary or mandibular incisors, the occlusal edges were used as reference points. Measurements were recorded on postoperative days 0, 2, and 7.

c) Edema assessment: facial edema was measured using the method described by Gabka and Matsumura. Three linear facial measurements were obtained in millimeters with a measuring tape: tragus to pogonion, tragus to oral commissure, and lateral canthus to mandibular angle. The mean of these three measurements was calculated to quantify edema. This assessment was performed preoperatively and on postoperative days 2 and 7.

d) Quality of life assessment: quality of life was evaluated using a questionnaire adapted from the OHIP-14 (APPENDIX D), consisting of 14 dichotomous (yes/no) questions addressing daily functional limitations. The questionnaire included items related to chewing and swallowing ability, dietary changes, alterations in taste, mouth opening, voice changes, speech intelligibility, facial appearance, sleep disturbances, and ability to perform work-related activities. The questionnaire was provided to participants on the day of surgery and completed on postoperative days 0, 2, and 7. At the conclusion of the evaluation period following the second intervention, participants also answered the question: “Which intervention did you perceive as resulting in greater postoperative improvement?”

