### 5.3 EDEMA

Time significantly affected postoperative edema ( $F_{(2,32)} = 10.34$ ,  $p < 0.001$ ), whereas treatment ( $F_{(1,16)} = 0.516$ ,  $p = 0.48$ ) and the interaction between factors ( $F_{(2,32)} = 1.533$ ,  $p = 0.23$ ) did not.

Both groups exhibited greater edema on postoperative day 2 compared with baseline (Group A:  $123.0 \pm 5.1$  vs.  $126.2 \pm 7.8$ ,  $p = 0.02$ ; Group B:  $123.1 \pm 7.1$  vs.  $126.3 \pm 7.5$ ,  $p = 0.005$ ). No significant differences were observed between baseline and postoperative day 7 in either Group A ( $123.0 \pm 5.1$  vs.  $126.1 \pm 7.8$ ;  $p = 0.86$ ) or Group B ( $123.1 \pm 7.1$  vs.  $123.5 \pm 8.7$ ;  $p = 0.71$ ), indicating resolution of edema by the end of the evaluation period in both groups (Table 4).

[figure not shown]

Table 4: Average of edema values on days 0, 2 and 7 post-op.

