## 5.4 QUALITY OF LIFE

Among the 14 items of the OHIP-14 questionnaire, only three showed significant differences between groups. Regarding mouth opening, 31% of participants in Group A still reported difficulty opening the mouth on postoperative day 7, compared with 23.5% in Group B. Concerning sleep disturbances, Group A showed an approximate 40% reduction in complaints between postoperative days 2 and 7, whereas Group B demonstrated a reduction of approximately 66.6%.

When participants were asked which intervention resulted in greater postoperative improvement, all patients who underwent the control protocol in the first surgery (100%) preferred the cryotherapy intervention. Among those who received cryotherapy during the first procedure, 83% also indicated preference for the cryotherapy side.

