Regarding quality of life, three variables demonstrated notable percentage differences between groups. First, participants in the cryotherapy group reported less difficulty sleeping, likely reflecting the superior pain control achieved with this intervention. Second, when asked which procedure resulted in greater postoperative improvement, all 11 participants who initially underwent the control protocol reported greater improvement following the cryotherapy intervention. Participants described a reduction in burning or heat sensations and perceived a faster recovery trajectory compared with the non-cryotherapy procedure, consistent with the pain outcomes shown in Table 1. Third, patients treated with cryotherapy reported less difficulty opening their mouths, which appears to be closely related to their lower subjective pain perception. As demonstrated in Tables 1 and Graphic 2, the greater reduction in pain intensity in the test group was reflected in a lower proportion of participants reporting functional limitation.

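### The claim of better sleep with cryotherapy does not follow from section 5.4, which gives only within-side falls from day 2; the count of three significant items among 14 includes a question outside the 14 and has no stated test

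*Combined protocol and SAP*

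**What the plan says.** **Schedule.** Section 4.7 places the assessments "on postoperative days 0 (day of surgery), 2, and 7" and says of the questionnaire: "The questionnaire was provided to participants on the day of surgery and completed on postoperative days 0, 2, and 7". The columns of the form in Appendix D are pre-op, second day and seventh day.

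**Treatment window.** Under section 4.6 the ice begins straight after surgery and is "continued for the first 12 postoperative hours". Day 2 is therefore a post-treatment visit.

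**Planned analysis.** For the questionnaire, section 4.8 plans percentages and names no test.

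**Results.** Section 5.4 opens: "Among the 14 items of the OHIP-14 questionnaire, only three showed significant differences between groups". On sleep it says "Group A showed an approximate 40% reduction in complaints between postoperative days 2 and 7", and gives about 66.6% for Group B. On mouth opening it gives 31% (A) and 23.5% (B) with difficulty at day 7. No p-value appears.

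**Claims.** The Discussion states that "participants in the cryotherapy group reported less difficulty sleeping". The abstract lists sleep, mouth opening and perceived improvement as the three significant items.

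**The concern.** A percentage fall within one side shows how far that side moved from its own day-2 level. It does not show which side had fewer complaints at day 2 or at day 7. A side that starts with more complaints can show the larger fall and still end level or worse. Day 2 also comes after the ice period, so the reference value may already carry any treatment effect.

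The third of the three items is the question about which intervention gave more improvement. Section 4.7 describes it as asked once, after the second intervention, and it is not among the 14 questions in Appendix D. At most two of the 14 items are therefore reported as differing, and nothing in sections 4.8 or 5.4 says how significance was judged.

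At stake are a treatment benefit stated in the abstract and Discussion, and the reader's view of how many questionnaire items were affected.

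**Working it through.** **Inputs.** 17 patients, each contributing both sides (section 4.4); falls of about 40% (A) and about 66.6% (B) from day 2 to day 7 (section 5.4); 31% and 23.5% for mouth opening at day 7 (section 5.4); significance level 0.05 (section 4.8).

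**1. Can the stated falls be reproduced?** Not directly, because no sleep counts are given. Read as percentage points out of 17, 66.6% cannot occur (11/17 = 64.7%, 12/17 = 70.6%). The likely reading is relative: fall = (day-2 count − day-7 count) / day-2 count. Assuming one item and 17 answers per side, the exact fits are:

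- A, 40%: 5 to 3, 10 to 6, 15 to 9.
- B, two thirds: 3 to 1, 6 to 2, 9 to 3, 12 to 4, 15 to 5.

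**2. What do they imply at day 7?** Each cell gives day-7 complaints, A v B.

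| | B 3 to 1 | B 6 to 2 | B 9 to 3 | B 12 to 4 | B 15 to 5 |
|---|---|---|---|---|---|
| A 5 to 3 | 3 v 1 | 3 v 2 | 3 v 3 | 3 v 4 | 3 v 5 |
| A 10 to 6 | 6 v 1 | 6 v 2 | 6 v 3 | 6 v 4 | 6 v 5 |
| A 15 to 9 | 9 v 1 | 9 v 2 | 9 v 3 | 9 v 4 | 9 v 5 |

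Ice has fewer complaints in 12 of 15, the same in 1 and more in 2. At day 2, ice has fewer in 8, the same in 1 and more in 6. If *approximate* is taken to allow 37.5% to 42.5% in A, there are 40 combinations, and the day-7 split is 36 fewer, 2 equal, 2 more.

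**3. Could the sleep contrast be significant?** Comparing the share of day-2 complaints that resolved, Fisher's exact p runs from 0.24 to 1.0 over the 15 combinations. This ignores the pairing and is only illustrative. For a paired day-7 comparison, the smallest possible exact McNemar p arises when every discordant pair points the same way: p = 2 × 0.5^d, where d is the difference in counts. With d = 5 this is 0.0625 and with d = 6 it is 0.031. Only 9 v 1 (d = 8, p = 0.008), 9 v 2 (d = 7, p = 0.016) and 9 v 3 (d = 6, p = 0.031) could fall below 0.05. A significant day-7 result is thus possible in 3 of the 15 combinations and impossible in the other 12.

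**4. Mouth opening.** 23.5% is 4/17. 31% cannot be obtained out of 17 (5/17 = 29.4%, 6/17 = 35.3%). With up to 17 answers, only 5/16 = 31.25% and 4/13 = 30.8% round to it.

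- With 5/16, the 16 complete pairs hold 3 or 4 ice-side complaints, so d is at most 5 − 3 = 2 and p is at least 2 × 0.5^2 = 0.5. The unpaired Fisher p for 5/16 v 4/17 is 0.71.
- With 4/13, d is at most 4 − 0 = 4 and p is at least 2 × 0.5^4 = 0.125.

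Neither reading allows a paired day-7 difference below 0.05.

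**5. Timing labels.** Section 4.7 says day 0 and Appendix D says pre-op. For edema, section 4.7 says "This assessment was performed preoperatively and on postoperative days 2 and 7", while Table 4 is captioned "Average of edema values on days 0, 2 and 7 post-op". So the document elsewhere labels a preoperative value day 0.

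**The case against.** The best defence is that most combinations favour ice. The two that go against it need 12 or 15 of 17 patients complaining on the ice side at day 2 against 5 of 17 on the control side, which sits awkwardly with the lower ice-side pain reported on days 1 and 3. That stands, and it rules out any suggestion that ice worsened sleep. It does not supply the missing comparison. It is also true that the Conclusion section does not mention sleep and that the Discussion speaks of percentage differences; the abstract, however, calls the items significant.

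A reader might infer more than the documents support, in three ways:

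- *That the first questionnaire was completed after surgery and is no baseline.* Day 0 is defined only as the day of surgery, the form itself says pre-op, and preoperative edema is also labelled day 0. The likely explanation is one visit with loose labelling. The Discussion's mention of immediate postoperative measurements leaves enough doubt to ask, but not to assert.
- *That the label mismatch, or the unused pre-op column, is why the sleep claim fails.* It is not. In a randomized split-mouth design, a paired comparison of sides at day 2 or day 7 could support the claim without a baseline.
- *That comparing mouth opening at day 7 alone is a flaw.* A between-side comparison at a post-treatment visit is legitimate. What is missing there is the denominator and the test. Restricting the analysis to complaints absent before surgery would be a preference, not a requirement.

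**Conclusion.** The point holds in this form: the sleep benefit is not shown by the figures given, because section 5.4 reports relative change within each side and never the level on each side or a comparison between them. The stated falls fit fewer, equal or more day-7 complaints with ice (12, 1 and 2 of 15 exact combinations). This rests on one item, 17 answers per side and a relative reading of the percentages. Appendix D has two sleep items, and section 5.4 does not say which was used or whether they were combined. The combinations are a list of what is possible and carry no probabilities.

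Separately, the statement on three of 14 items should be at most two items plus the preference question, and *significant* has no stated basis. For mouth opening at day 7, no denominator up to 17 that gives 31% would allow a significant paired difference. The day-0 and pre-op labels need only a clarification.

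**What to change.** - In sections 4.8 and 5.4, give yes/no counts with denominators by side at each visit for the mouth-opening item and for both Appendix D sleep items (trouble sleeping, waking at night). Explain the denominator behind 31%.
- Compare sides at day 2 and day 7 with an exact McNemar test, and say that the test was added after the results were known.
- Stop using relative falls from day 2 as evidence of better sleep. If the paired comparison does not support them, withdraw the sleep statement and the word *significant* from the abstract, section 5.4 and the Discussion. With 17 pairs, at least 6 discordant pairs all in one direction are needed for p < 0.05, so a non-significant result should be worded as not shown, not as no effect.
- Replace the count of three among the 14 items with at most two items plus a separately reported preference question.
- State whether the first questionnaire was completed before surgery, and align section 4.7 with Appendix D.

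The cost is one re-tabulation of forms that should already be in hand, and some rewording. The downside is that the sleep claim may have to be withdrawn.

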#### 4.8 STATISTICAL ANALYSIS

Data normality was assessed using the Kolmogorov–Smirnov test. Parametric analyses were applied to compare groups (control side vs. test side) and postoperative time points (from day 0 to day 7). Continuous variables, including pain intensity (VAS scores), maximum mouth opening (mm), and facial edema (mm), were expressed as means  $\pm$  standard deviation (SD).

A two-way repeated-measures analysis of variance (ANOVA), followed by Fisher's least significant difference (LSD) post hoc test, was used to evaluate the main effects of time and treatment, as well as their interaction, for pain intensity, trismus, and edema. Pain reports were also qualitatively analyzed based on the frequency distribution of pain categories (no pain, mild pain, moderate pain, and severe pain) for both groups.

Associations between pain intensity and trismus or edema were assessed using Pearson's correlation coefficient. Trismus and edema were additionally evaluated using the formulas (Baseline – Postoperative) and (Postoperative – Baseline), respectively. Qualitative data related to quality of life were presented as percentages.

All statistical analyses were performed using SPSS software (version 20.0; IBM Corp., Armonk, NY, USA). Statistical significance was set at  $P < 0.05$ .

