## ABSTRACT

Third molar extraction is a common oral surgical procedure often associated with postoperative pain, edema, and functional limitation. Effective postoperative management plays a key role in minimizing morbidity and promoting patient comfort. Strategies such as cryotherapy may contribute to improved recovery and quality of life after surgery. **Objective:** to investigate the effects of cryotherapy on postoperative outcomes (pain intensity, edema, trismus and quality of life) following mandibular third molar extraction. **Materials and Methods:** This study was designed as a randomized split-mouth clinical trial. The sample consisted of 17 patients (34 mandibular third molars with equivalent levels of impaction) who underwent bilateral surgical extraction. The surgical sites were allocated into two groups according to postoperative care: Group A (control side—without cryotherapy) and Group B (test side—with postoperative cryotherapy using ice packs). All intraoperative and postoperative procedures, instructions, and medications were identical for both groups. Patients were evaluated for pain intensity, trismus severity, presence of edema, and quality of life for up to seven days postoperatively (D7). The evaluator was aware of the postoperative intervention applied. Repeated-measures ANOVA was used to analyze each outcome variable, and associations between continuous variables were assessed using Pearson's correlation test. Statistical significance was set at 5% ( $P < 0.05$ ). **Results:** Overall, postoperative pain intensity was lower in patients who received cryotherapy. Group A reported significantly higher pain intensity on postoperative days 1 and 3. No signs of trismus were observed in Group B at the end of the follow-up period, whereas Group A presented restricted mouth opening at D7. Both groups exhibited edema on postoperative day 2 (D2); however, complete regression of edema by D7 was observed only in Group B. Additionally, a significant association between pain intensity and trismus severity was identified in Group A at D7. Quality-of-life assessment revealed significant differences in three questionnaire items favoring Group B, including greater perceived improvement, better mouth opening, and reduced difficulty sleeping. **Conclusion:** The findings suggest that postoperative cryotherapy is effective in reducing pain intensity and trismus following mandibular third molar extraction. Moreover, this physical therapy modality appears to enhance pain tolerance and patients' self-perceived healing.

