### 4.1 SAMPLE CALCULATION

The sample size was calculated based on a previously published study, which adopted a significance level of 5% ( $p < 0.05$ ), a statistical power of 90%, and a margin of error of 5%, resulting in a required sample size of 40 surgical sites. In the baseline study, pain perception during local anesthesia was compared between acupressure and cryotherapy using a split-mouth design involving 20 patients. Similarly, the present study employed a split-mouth design, with procedures performed on 20 patients, yielding a total of 40 surgical sites.

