### 5 RESULTS

#### 5.1 POSTOPERATIVE PAIN INTENSITY

The analysis demonstrated significant main effects of treatment ( $F_{(1,16)} = 5.063$ ,  $p = 0.039$ ) and time ( $F_{(7,112)} = 6.254$ ,  $p < 0.001$ ) on postoperative pain intensity (Table 1). Overall, pain scores were higher in Group A than in Group B ( $2.0 \pm 1.2$  vs.  $1.3 \pm 1.1$ ;  $F_{(1,16)} = 5.063$ ,  $p = 0.039$ ).

[figure not shown]

[figure not shown]
Table 1: Average pain levels on every post-operative day for each group. (\*) indicates statistical differences between control and test groups.

In Group A, pain intensity was significantly higher on postoperative days 1 ( $3.59 \pm 0.59$ ;  $p = 0.014$ ) and 3 ( $3.24 \pm 0.55$ ;  $p = 0.005$ ) compared with day 0 ( $1.35 \pm 0.54$ ). No significant differences were observed between day 0 and the remaining postoperative time points ( $p > 0.05$ ).

[figure not shown]
On the test side (Group B), no significant differences in pain intensity were observed between day 0 and any postoperative evaluation ( $p > 0.05$ ), suggesting that cryotherapy effectively prevented postoperative pain exacerbation.

A significant interaction between treatment and time was also observed ( $F_{(7,112)} = 2.689$ ,  $p = 0.013$ ). Pain intensity was higher on postoperative day 1 (Group A:  $3.59 \pm 0.59$  vs. Group B:  $2.12 \pm 0.42$ ;  $p = 0.017$ ) and day 3 (Group A:  $3.24 \pm 0.55$  vs. Group B:  $1.29 \pm 0.33$ ;  $p = 0.007$ ) in the control group compared with the cryotherapy group.

Postoperative pain was absent in 29.4% of control cases and 44.1% of cryotherapy cases. Mild pain was reported by 50.0% of participants in Group A and 47.8% in Group B, whereas moderate pain occurred in 16.9% and 7.4% of cases, respectively. Severe pain was reported by 3.7% of control cases and 0.7% of cryotherapy cases (Graphics 1 and 2).

Graphic 1: Prevalence of reports of moderate to severe pain (4-10 in visual analogic scale) in the total number of reports of pain (1-10 in visual analogic scale) in the control group after day 2 (last day of analgesic medication).

12

Graphic 2: Prevalence of reports of moderate to severe pain (4-10 in visual analogic scale) in the total number of reports of pain (1-10 in visual analogic scale) in the test group after day 2 (last day of analgesic medication).

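### Three quality-of-life results are called significant with no test behind them, and the daily pain p-values are unadjusted LSD: under family-wise control day 1 does not hold and day 3 is borderline

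*Combined protocol and SAP*

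**What the plan says.** **Quality of life.** Section 4.8 states: "Qualitative data related to quality of life were presented as percentages". It names no test. The abstract reports: "Quality-of-life assessment revealed significant differences in three questionnaire items favoring Group B". Section 5.4 says that three of the 14 items differed significantly, again without a test or p-value. The Discussion describes the same three results only as noteworthy differences in percentages. It lists them as sleep, the preference question and mouth opening.

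**Daily pain.** Section 4.8 uses parametric analyses to "compare groups (control side vs. test side) and postoperative time points (from day 0 to day 7", judged at 5%. After the ANOVA, Fisher's "least significant difference (LSD) post hoc test, was used to evaluate the main effects of time and treatment". Section 5.1 states: "A significant interaction between treatment and time was also observed" (F(7,112)=2.689, p=0.013). It then reports the control side as higher on day 1 (3.59 against 2.12, p=0.017) and day 3 (3.24 against 1.29, p=0.007). The abstract says: "Group A reported significantly higher pain intensity on postoperative days 1 and 3", without qualification.

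**The concern.** A result can be called significant only if it was tested. The quality-of-life results were planned as description, and the report itself is divided on what they are. The Discussion also uses the mouth-opening item to corroborate its trismus finding, so the wording carries weight beyond the abstract.

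For pain, a significant omnibus test before LSD protects the family-wise error rate for three means, but not for eight daily contrasts. If all eight were null and independent, testing each at 5% would give at least one false positive with probability 1 − 0.95^8 = 33.7%. A reader of the abstract would take both single-day claims as established, with no sign that they are two of eight unadjusted comparisons.

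**Working it through.** **Reproducing the printed figures.** The upper tail of F gives 0.0389 for F(1,16)=5.063 (printed 0.039) and 0.0130 for F(7,112)=2.689 (printed 0.013). The degrees of freedom fit eight days and 17 patients: 7 = 8 − 1, and 112 = 7 × 16.

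**Mouth opening, day 7 (5.4).** 4/17 = 23.5%. The figure of 31% fits 5/16 (31.25%); 5/17 would be 29.4%.
- Fisher's exact test: 5/16 against 4/17 gives p=0.71; 5/17 against 4/17 gives p=1.0.
- The data are paired, so exact McNemar is the proper test. A net difference of one patient gives 1.0 whatever the number of discordant pairs.
- If one control-side answer is missing, the pairs could be 5 against 3, a net difference of two. With discordant pairs (2,0), (3,1), (4,2) and (5,3), p is 0.50, 0.625, 0.688 and 0.727. The smallest possible value is 0.50.

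**Sleep (5.4).** The text gives reductions from day 2 to day 7 of about 40% (control) and 66.6% (ice). These are two within-side changes, not a between-side comparison, and no counts are given. Counts that fit include 5 to 3, 10 to 6 or 15 to 9 on the control side, and 3 to 1, 6 to 2, 9 to 3, 12 to 4 or 15 to 5 on the ice side. A day-7 paired test could then give anything from 2 × 0.5^8 = 0.008 (9 against 1, all eight discordant pairs one way) to 1.0. Appendix D has two sleep items, and the text does not say which was used.

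**Preference (5.4, Discussion).** All 11 control-first patients chose ice, as did 83% of the other 17 − 11 = 6, that is 5. The total is 16/17. Two-sided sign test: 2 × (17 + 1)/2^17 = 0.0003. Section 4.7 defines this as a separate closing question, so it is not one of the 14 items.

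**Daily pain, Holm.** Assume days 3 and 1 have the two smallest p-values. With m days, day 3 becomes m × 0.007 and day 1 becomes (m − 1) × 0.017.

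| Family | Day 3 | Day 1 |
|---|---|---|
| 8 days (0 to 7) | 0.056 (0.052 to 0.060) | 0.119 (0.116 to 0.123) |
| 7 days (1 to 7) | 0.049 (0.046 to 0.053) | 0.102 (0.099 to 0.105) |

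Brackets show the effect of rounding in the printed p-values. Day 1 would pass only in a family of three days or fewer: 2 × 0.017 = 0.034, but 3 × 0.017 = 0.051 with four.

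**Allowing for correlation between days.** Holm ignores correlation, so it can be conservative. A step-down max-t simulation used 17 pairs, 200,000 null runs per setting and equal correlation between days. Over eight days it gave:

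| Correlation | Day 3 | Day 1 |
|---|---|---|
| 0 | 0.055 | 0.113 |
| 0.3 | 0.052 | 0.105 |
| 0.5 | 0.046 | 0.093 |
| 0.7 | 0.038 | 0.075 |

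The between-day correlation is not reported, so this is a range and not an estimate.

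**Alternative reading of the abstract.** If its sentence means the control side against its own day 0 (p=0.014 and 0.005 in 5.1), Holm over seven comparisons gives 7 × 0.005 = 0.035 for day 3 and 6 × 0.014 = 0.084 for day 1. Day 1 fails on this reading too.

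**The case against.** The strongest reply concerns pain. The plan named LSD at 5%, the interaction was significant, and the report applied that rule as stated. No section promises family-wise control, so calling day 1 not significant outright would substitute a criterion chosen after the results. That stands. Section 4.8 need not change, and Holm belongs beside LSD as a labelled sensitivity analysis.

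It is also fair that day 3 may pass with all eight days counted if the days are moderately correlated, so Holm 0.056 alone would show the conservative end. Leaving out day 0 would also bring day 3 under 5%. However, ice was started immediately after surgery on that day, so the omission needs a reason, and rounding of p=0.007 could reverse the result.

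A reader might infer that six p-values were withheld. The documents do not support this: Table 1 is a figure that cannot be read here and is captioned as marking between-group differences.

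A reader might also infer that the pain result as a whole falls. It does not, because the treatment main effect is a single test over all days.

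Nor do the documents show that every quality-of-life result is null. Preference is strong, though patients knew which side had ice, and sleep cannot be tested either way. None of these replies supplies a test for the quality-of-life wording.

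**Conclusion.** The point holds in two parts of different strength.

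The quality-of-life part is firm. Significance is claimed for three results with no planned or reported test, against the report's own plan and Discussion. Mouth opening cannot be significant on the printed percentages, sleep cannot be checked, and preference lies outside the 14 items.

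The pain part is a qualification, not a breach of the plan. Both days meet the stated LSD rule. Day 1 is not supported under family-wise control: Holm gives 0.119 or 0.102, and max-t over eight days about 0.07 to 0.11. Day 3 is borderline: about 0.046 to 0.056 over eight days across Holm and max-t with correlation up to 0.5, and Holm 0.049 over seven. This assumes two-sided tests and that the six p-values not in the readable text exceed 0.017.

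The overall pain effect keeps its printed p=0.039, and the Conclusion makes no day-specific pain claim.

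**What to change.** 1. Delete the word significant for the quality-of-life results in the abstract and 5.4. Give counts and denominators per item, side and day, and name the sleep item used. Report preference (16/17) separately from the 14 items, as an unblinded result.
2. Label the daily pain p-values as unadjusted LSD. Print all eight between-side values with Holm-adjusted values beside them, marked as a post hoc sensitivity analysis with the family stated.
3. Qualify the abstract and 5.1. If the six other p-values are larger, suitable wording would be: differences were largest on days 1 and 3 (unadjusted LSD p=0.017 and 0.007; Holm over eight days 0.119 and 0.056); under family-wise control day 1 does not hold and day 3 is borderline.

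The cost is some rewording and two tables from data already collected. The wording becomes less favourable, and the adjusted values carry less power for single days.
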